### **A. Specific Aims**

Tibial plafond fractures account for 7-10% of all tibia fractures and are potentially devastating injuries that continue to provide treatment challenges for orthopaedic traumatologists. While most trauma centers have adopted a staged protocol with initial external fixation followed by delayed internal fixation after soft tissue recovery, patients continue to report relatively poor physical and psychosocial outcomes. A significant reduction in range of motion is commonly observed after operative fixation of tibial plafond fractures, specifically loss of dorsiflexion. If the decrease in dorsiflexion is severe enough, it is termed equinus contracture and can pose functional limitations and contribute to additional lower limb pathologies in those suffering from it. Botulinum toxin A has been shown to be effective in increasing dorsiflexion in children with equinus contracture from muscle spasticity from cerebral palsy. More recently, promising results have been seen in using Botulinum toxin A in the treatment of contractures following Achilles tendon repair and total knee arthroplasty. The purpose of this study is to evaluate the effect of Botulinum toxin A injections into the gastrocsoleus complex on ankle dorsiflexion following internal fixation of tibial plafond fractures.

Specific Aim 1: To determine if the use of Botulinum toxin A intramuscular injections of the gastrocsoleus complex in patients with operatively treated tibial plafond fractures will result in increased ankle dorsiflexion when compared to controls.

Hypothesis 1: The group treated with Botulinum toxin A injections will have increased ankle dorsiflexion when compared to controls at 6 and 12 months.

Specific Aim 2: To determine if the use of Botulinum toxin A injections in patients with operatively treated tibial plafond fractures will lead to increased ankle functionality as measured by the FAAM, and quality of life as measured by the SF-36, when compared to controls.

Hypothesis 2: The group treated with Botulinum toxin A injections will report more positive health-related quality of life when compared to controls at 6 and 12 months.

Specific Aim 3: To determine if the use of Botulinum toxin A injections in patients with operatively treated tibial plafond fractures will lead to a higher proportion of patients achieving at least 10 degrees of dorsiflexion when compared to controls.

Hypothesis 3: The group treated with Botulinum toxin A injections will be more likely to achieve 10 degrees or more of ankle dorsiflexion at 6 and 12 months.

We plan to enroll 20 patients (N=10 treatment, N=10 controls) in a pilot study to test procedures and collect preliminary data. While this pilot study will likely not have sufficient power to definitively address the specific aims and hypotheses, the preliminary data collected will provide information to plan future work.

**B. Background and Significance** Defined as a fracture of the distal end of the tibia that involves a significant portion of the weight-bearing articular surface and overlying metaphysis, tibial pilon fractures are difficult orthopaedic injuries to treat. This fracture pattern is most commonly caused by motor vehicle collisions, falls, and sporting accidents. These mechanisms produce high energy axial loads at the ankle joint causing significant articular comminution, bone loss, and soft tissue injury traditionally resulting in a high rate of unsatisfactory outcomes.

**B.1 Management of Pilon Fractures:** Initially considered unsuitable for surgery, the treatment of tibial plafond fractures has evolved significantly over the last 50 years to a point where most centers are utilizing a staged fixation approach. The staged method employs primary external fixation to restore length and alignment of the extremity while allowing the soft tissues to heal. Once the tissues permit, an open approach is used to provide sufficient visualization of the fracture for anatomic reduction of the articular surface and cancellous bone grafting if necessary. Rigid internal fixation with or without cancellous bone grafting is paramount in maintaining joint line congruity, preventing malunions, and allowing for early range-of-motion across the joint, thus providing better functional outcomes compared to other methods such as external fixation with or without limited internal fixation.

**B.2 Current Difficulties in Treating Pilon Fractures:** Despite widespread usage of a staged protocol for this injury, good to excellent results are still difficult to attain. Recent studies consistently report “relatively poor physical and psychosocial outcomes” with persistent and severe sequelae. Pollack and colleagues noted that at 3-year follow-up, patients presented with significantly poorer health related outcome scores than age and gender-matched norms. Large proportions of patients with this type of injury present with significant stiffness, swelling, pain, and difficulties with retaining employment, showing that there is still work to be done to improve the outcomes of this devastating injury.

**B.3 Loss of Dorsiflexion:** Limited range of motion is a common and potentially debilitating result of these often severe articular injuries. A minimum of 10 degrees of dorsiflexion is required for normal gait mechanics and loss of this dorsiflexion is termed equinus contracture. Equinus contracture can result in functional limitations as well as be a contributing factor to seemingly unrelated lower limb pathologies including strains, plantar fasciitis, hallux valgus, stress fractures, adult-acquired flat foot, plantar fasciitis, Achilles tendonitis, Charcot arthropathy, diabetic foot ulceration, and metatarsalgia. Gait analysis studies examining limited dorsiflexion in the ankle joint has shown that patients with less than 10 degrees of dorsiflexion begin to experience abnormal stresses at multiple other lower extremity joints. In addition to contributing to these other pathologies, loss of dorsiflexion and pain are the only two independent variables shown to significantly limit functionality in patients recovering from ankle fractures.

Recent studies following outcomes on tibial plafond fractures have repeatedly shown dorsiflexion to be impacted. Grose and colleagues found the average dorsiflexion in their cohort to be 9 degrees with only 25% achieving greater than 10 degrees of dorsiflexion. Patients treated by Patterson and Cole achieved only 7 degrees of dorsiflexion after staged internal fixation. Marsh et al. measured an average dorsiflexion of 10 degrees with 50% of patients failing to reach at least 10 degrees of dorsiflexion, even after excluding those who underwent amputation or arthrodesis. Functional limitations such as difficulty climbing up stairs, walking up hills, and squatting to pick up objects are commonly reported problems following this injury, all of which reflect a loss of dorsiflexion. Clearly, stiffness is a ubiquitous problem in this population and carries with it the sequela of impaired functionality while contributing to other lower extremity problems.

**B.4 Treatment Options for Limited Range of Ankle Motion:** Once acquired, equinus contractures can be very difficult to treat. Physiotherapy and stretching are the first line therapy to improve this condition, but often only play a limited role in the correction of this condition. Surgical options remain the mainstay treatment for contractures that are causing significant functional impairment. Achilles tendon lengthening is one surgical option that addresses equinus contracture by lengthening the Achilles tendon by utilizing a Z-lengthening technique. This procedure has a long recovery time and carries with it the risk of skin slough, Achilles tendon rupture, and discomfort with shoewear. Because the Achilles tendon accounts only for 3-5% of the contracture, there is also concern that lengthening the tendon reduces its moment-generating capacity due to the gastrocsoleus' new position on the sarcomere length-strength curve, resulting in weakness in plantarflexion. Additionally, this procedure also carries with it the risk of over lengthening causing a profound loss of strength and resulting in a heel gait pattern.

Other surgical options, such as the gastrocnemius recession, have been gaining popularity as an alternative to Achilles tendon lengthening in the treatment of equinus contractures, because it is able to address the contracture without resulting in loss of strength. One such technique, termed the Strayer recession, is performed by separating the gastrocnemius from the soleus and transecting it just proximal to the gastrocnemius-soleus aponeurosis. This allows the gastrocnemius muscle to retract proximally providing increased dorsiflexion. This procedure produces excellent results by achieving an average increase in dorsiflexion of 14-18 degrees, but it is not without complications. Sural neuropathy is a common complication of this procedure, either due to excessive retraction on the nerve at the time of surgery or proximal and distal tethering of the nerve within the gastrocsoleus complex during the release. Even though 42.5% of sural nerves run superficial to the fascia effectively protecting them from laceration during the release, sural and saphenous nerve lacerations can and do occur. Finally a significant number of patients report dissatisfaction with the scar left from the surgery which can pucker due to soft tissue adhesions, and exacerbated by retraction of the gastrocnemius muscle belly. Equinus contractures acquired after tibial plafond fractures are so problematic that some centers have advocated for performing a Strayer recession prophylactically at the time of fixation to prevent the development of such contractures.

**B.5 Botulinum Neurotoxin:** Botulinum toxin A (Botox) is an extremely potent neurotoxin produced by the bacterium *Clostridium botulinum* that results in transient flaccid muscle paralysis. To date, Botulinum toxin A and B are approved for use by the U.S. Food and Drug Administration for treatment of (1) chronic migraine headaches, (2) upper limb spasticity, (3) cervical dystonia, (4) strabismus and blepharospasm, (5) severe primary axillary hyperhidrosis, (6) and moderate to severe glabellar lines. In the orthopaedic literature, multiple potential indications have been identified including shoulder dislocations, adhesive capsulitis, talipes equinovarus, plantar fasciitis, torticollis, knee flexion contractures, lateral epicondylitis and cerebral palsy; all of which are currently considered "off-label."

**B.6 Botox Use for Treating Equinus Contractures:** Among its many uses, Botox has been used in the treatment of a variety of range of motion limiting conditions. For many years, botulinum toxin has been used with great success in treating equinus deformity in children with cerebral palsy. Several double-blind prospective studies have reported an increase in ankle joint mobility during stance and swing phases with the use of Botox.

Based on the success seen in the treatment of equinus contractures in children with cerebral palsy, botulinum toxin has been used in the treatment of equinus contractures following Achilles tendon repair. Reuter and others treated 8 patients with equinus contractures after Achilles tendon repair with intramuscular Botox injections and physiotherapy. All patients experienced significant increases in dorsiflexion which remained present at their 2 year follow-up with no adverse events identified.

**B.7 Botox Use for the Prevention of Equinus Contractures:** In addition to treating equinus contractures due to spasticity, Botox has been shown to prevent the occurrence of contractures in animal models. In 1994, Cosgrove and Graham used a spastic mouse model commonly used to mimic cerebral palsy, to show that intramuscular injections into the calf muscles prevented the formation of contractures. They found that mice who received placebo as opposed to intramuscular Botox had calf muscles which were 16% shorter than those who received Botox, supporting the theory of using Botox to prevent contracture formation.

**B.8 Botox Use for Treating Flexion Contracture Following Total Knee Arthroplasty:** Recently, Botox has been used with great success in the treatment of flexion contractures following total knee arthroplasty. After an initial report on the successful treatment of flexion contracture following total knee arthroplasty in a patient with Parkinson's syndrome, Seyler and colleagues utilized botulinum toxin to treat 11 more patients with flexion contracture following total knee arthroplasty. Their results were extremely promising by showing clinical improvement in all 9 patients who had primary total knee arthroplasties. The only two failures were in patients who acquired their contractures after *revision* total knee arthroplasties. The patients who experienced the improvement maintained their increased range of motion and desirable outcomes at the time of two year follow-up, leading the authors to conclude that Botox therapy may be appropriate therapy for the treatment of flexion contractures following primary total knee arthroplasty. An additional investigation is currently under way using a larger cohort of patients and is currently showing promising preliminary results.

**B.9 Botox Reduces Pain and Spasm:** Part of the theory on why Botox has been effective in alleviating these contractures is that the temporary muscle paralysis reduces pain and muscle spasms which can impede therapeutic stretching regimens. There is also increasing evidence that Botox has anti-nociceptive properties that may be due to inhibiting the release of pain mediators in addition to decreasing muscle spasms. Muscle spasms are commonly experienced following fracture fixation and can be a source of significant discomfort, which can interfere with rehabilitation by causing pain and limiting range of motion. Neutralization of this phenomenon may result in better functional outcomes due to more effective rehabilitation and stretching techniques employed postoperatively.

Even after the initial spasms have subsided, Botox may aid in the prevention of contracture and help facilitate therapeutic stretching techniques by reducing the basal tone of the plantar flexors. Even at rest, muscles exert a baseline tone to maintain posture and joint position. By weakening or paralyzing the gastrocsoleus complex, there would be an imbalance in muscular tone in the lower leg pulling the foot into a more dorsiflexed position even at rest. This will also reduce voluntary and involuntary guarding during stretching exercises, thus improving the effectiveness of rehabilitation regimens.

**B.10 Summary:** Based on Botox's ability to reduce pain and postoperative muscular spasms while at the same time eliminating resting basal tone of the primary plantar flexors about the ankle, it is felt that intramuscular injections will be beneficial in aiding therapeutic stretching exercises which is essential for maintaining ankle range of motion. These exercises will be started approximately 2 weeks after the time of definitive fixation which is well within the 8-10 weeks of maximal effect seen with intramuscular botulinum toxin injections. Botulinum toxin injections have not only been shown to prevent the development in of contractures, but also used to treat contractures which have already formed. The purpose of this study is to evaluate the effect of Botulinum toxin A injections into the gastrocsoleus complex on ankle dorsiflexion after staged internal fixation of tibial plafond fractures. If Botulinum toxin A proves effective, this approach could have a significant impact on the practice and outcomes of orthopaedic surgery and will allow for treatment and prevention of equinus contracture without the morbidity associated with an additional surgical procedure.

## **C. Preliminary Studies**

While the investigators have not completed preliminary studies specifically addressing the effects of Botulinum toxin A on tibial plafond fractures, several members have had prior experience in prospective randomized studies in this patient population.

The principal investigator published a multicenter study entitled: “Indometacin as prophylaxis for heterotopic ossification after operative treatment of fractures of the acetabulum” which involved a similar prospective double-blind placebo-controlled study design. The experience obtained from this study provides a valuable resource for successfully managing the proposed study.

The study implementation will be led by a PhD clinical researcher with experience coordinating randomized controlled trials funded by NIH, CDC, and the Robert Wood Johnson Foundation. The principal investigator’s orthopaedic clinical research team has successfully implemented and completed several randomized trials to date.

## **D. Research Design and Methods**

We will use a prospective double-blind randomized placebo-controlled study design. Subjects will be enrolled as inpatients or during the initial office visit by orthopaedic clinical research staff. After routine evaluation reveals that a patient meets the inclusion and exclusion criteria (below), informed consent will be obtained. Demographic data will be recorded. Patients will be block randomized by opaque, sealed-envelope to either a treatment group or a placebo group (N=20; N=10 treatment, N=10 placebo).

### **D.1 Inclusion and Exclusion Criteria**

#### Inclusion Criteria

- Patients 18 and older with a tibial plafond fracture to be treated by a staged protocol involving primary external fixation and definitive fixation within 3 weeks from the injury.
  - Non-definitive, interval procedures such as repeat irrigation and debridement and fibular fixation are allowed.

#### Exclusion Criteria

- Younger than 18 years of age.
- Significant traumatic brain injury or cognitive disability that would interfere with post-operative rehabilitation and study questionnaires.
- Nerve, vascular, or tendon injury of the lower leg: injury to the tibial or peroneal motor nerves, injury to the posterior tibial artery requiring repair, or laceration of tendons that are involved in plantar flexion or dorsiflexion of the ankle which require repair.
- History of prior lower extremity fracture to the tibia or ankle of the affected limb.
- Incarcerated patients.
- Patients unable or unwilling to return for follow-up examination.
- Pregnant or lactating patients.
- History of disease affecting the neuromuscular junction (ex: myasthenia gravis).
- Use of aminoglycoside antibiotics at the time of definitive fixation.
- Ipsilateral foot injury that will impair dorsiflexion exercises: Lisfranc injuries, fractures or dislocations of the talus, calcaneus, navicular, cuboid, cuneiforms, or metatarsals (phalanx fractures or dislocations will not be excluded).
- Patients receiving Botulinum Toxin A for other reasons.
- Patients with a known hypersensitivity to Botulinum toxin A.
- Gustilo Anderson type III B and C.
- Patients with a weight greater than 115 kg – to ensure proper injection locations.

- Patients taking non-depolarizing neuromuscular blocking agents (not including those used for general anesthesia).

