### **D.3 Methods**

Orthopaedic surgery attendings and residents will identify potential study candidates during the initial consultation based on the presence of a tibial plafond fracture. If the patient meets the inclusion and exclusion criteria (noted above), a member of the treatment team will discuss the study with eligible patients. If the patient expresses interest in the study, the physician will notify the research staff. Orthopaedic Clinical Research staff will describe study procedures in detail and go through the informed consent process to enroll the patient in the study. Patients will be informed of the “off-label” usage of botulinum toxin injections as well as the potential side effects.

Once informed consent is obtained and the patient is enrolled in the study, the attending surgeon will classify the fracture based on the AO/OTA classification system (Figure 1). Study participants will then be block randomized and assigned by sequentially numbered sealed opaque envelopes to one of the two treatment groups based on computerized selection: those who receive intramuscular botulinum toxin injections at the time of definitive fixation, and those who receive placebo. Patients with bilateral pilon fractures and no other lower extremity injuries of the tibia, ankle, or foot that would further impair dorsiflexion stretching or other

rehabilitation exercises will have each extremity randomized and evaluated separately. Patients with a unilateral tibial plafond fracture and no injury of the contralateral tibia, ankle, or foot will be placed in a subgroup of patients who will have their unaffected extremity examined for comparison. Patients with an injury to the contralateral extremity that would exclude them from this subset will have only the extremity with the pilon fracture analyzed.

[figure not shown]

Figure 1.

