##### **5.6.a.1 Botulinum Toxin Safety**

Botulinum Toxin A has been approved by the FDA for more than 20 years and has a long-established safety profile. When used correctly, the side effects of Botulinum Toxin type A injections are uncommon and usually mild and transient. Local side effects are the most common and are usually mild pain at the injection site and adjacent muscle weakness due to diffusion of the toxin across fascial barriers. Systemic side effects are very rare and include mild generalized weakness, urinary incontinence, constipation, and dysphagia; all of which are typically seen in susceptible individuals. Botox is contraindicated in patients with a history of neuromuscular disorder such as myasthenia gravis, and in patients receiving aminoglycoside antibiotics or non-depolarizing neuromuscular blocking agents, as these can all potentiate the effects of the toxin. It is also relatively contraindicated in patients with a history of pseudobulbar palsy and frequent chest infections for concern over aspiration pneumonia, an exceedingly rare, but serious side effect. These adverse events are not expected to cause problems based on our study design and patient population.

Of the local side effects, pain at the injection site is unlikely to be noticed by the patient as injections will be administered under general anesthesia and the patient's co-committent injury will likely dwarf any residual pain from the injection. The diffusion of Botox into adjacent muscle groups is not only inconsequential, but in-fact desired based on our study design. Although all injections will be made in the muscle belly of the gastrocnemius, diffusion into the deeper soleus muscle would provide additional weakness of the gastrosoleus complex and potentially result in better outcomes without causing additional functional impairment

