In order to minimize the occurrence of systemic side effects, the amount of Botox utilized in this study will be well below the maximum safe dose for Botox, 12U/kg, even if bilateral pilon fractures are both randomized to the treatment group. In addition, patients with a history of a neuromuscular disorder, who are receiving aminoglycoside antibiotics or non-depolarizing neuromuscular blocking agents, or women who are or may become pregnant will be excluded from this trial. Patients reporting dysphagia or aspiration are typically those undergoing injections for cervical dystonia, and may be considered a local side effect rather than a systemic one. Based on the remote injection site utilized for this study, dysphagia and aspiration are unlikely to be experienced. The average total dose of 200U of Botulinum Toxin A will be injected into the gastrocnemius of the effected extremity and was chosen based on the effective dose for the average gastrocnemius from other studies.

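### The exclusion lists name only disease of the neuromuscular junction, while the safety section contraindicates and excludes the wider class of neuromuscular disorders (minor consistency point)

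*Combined protocol and SAP*

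**What the plan says.** The exclusion criteria appear twice, in D.1 and in E.2, and the relevant line is the same in both: "History of disease affecting the neuromuscular junction (ex: myasthenia gravis").

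The safety section (numbered 5.6.a.1, within E.6) covers the same ground in two places:

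- It gives the contraindication: "Botox is contraindicated in patients with a history of neuromuscular disorder such as myasthenia gravis". Aminoglycosides and non-depolarizing blocking agents are in the same sentence, with one reason for all three: "as these can all potentiate the effects of the toxin".
- It then describes how the trial guards against systemic effects. That paragraph opens "In order to minimize the occurrence of systemic side effects", first cites the dose, and goes on: "In addition, patients with a history of a neuromuscular disorder". The sentence adds patients on the two drug classes and ends "women who are or may become pregnant will be excluded from this trial".

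Eligibility is decided on the listed criteria. Section D says "After routine evaluation reveals that a patient meets the inclusion and exclusion criteria (below), informed consent will be obtained", and D.3 says "If the patient meets the inclusion and exclusion criteria (noted above), a member of the treatment team will discuss the study with eligible patients". E.4 has the attending physician check the same criteria, and D.7 puts them online or on information cards for staff and residents.

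**The concern.** Disease of the neuromuscular junction is one part of the wider class of neuromuscular disorders. Read literally, the protocol gives two answers for a patient whose disorder lies outside the junction: the safety section excludes that patient, and the lists do not. A screener working from the lists or the cards alone would have no prompt to stop.

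What is at stake is the reliability of one stated safeguard. The safety section counts this exclusion among its steps against systemic side effects, on the ground that such conditions can strengthen the toxin's action. The step works as described only if the text used at screening carries it. D.8 plans to amend this protocol for a full trial, so an uncorrected line could carry over to more patients.

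**Working it through.** No arithmetic applies: no sample size, error rate, effect size or event rate in the plan depends on this line. The check is a comparison of texts.

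**Step 1. Set the terms side by side.**

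| Place | Class of disease named | Example given | Function |
|---|---|---|---|
| D.1 list | Disease of the neuromuscular junction | Myasthenia gravis | Exclusion criterion |
| E.2 list | Same as D.1 | Myasthenia gravis | Exclusion criterion |
| 5.6.a.1, contraindication | Neuromuscular disorder | Myasthenia gravis | Contraindication |
| 5.6.a.1, risk-reduction paragraph | Neuromuscular disorder | None | Statement of who is excluded |

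The two lists agree with each other. Both statements in the safety section use the wider class.

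**Step 2. Look for another listed item that fills the difference.** The nearest are injury to the tibial or peroneal motor nerves (trauma to the lower leg), brain injury or cognitive disability that would interfere with rehabilitation and questionnaires, and use of non-depolarizing blocking agents (a drug item). None covers a history of neuromuscular disorder outside the junction.

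**Step 3. Compare the contraindication sentence with the lists, item by item.**

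- Aminoglycosides: the same drug class is listed, limited to use at definitive fixation.
- Non-depolarizing blocking agents: the same drug class is listed, with an exception for general anesthesia.
- Neuromuscular disorder: the lists name a narrower class, the junction.

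The lists qualify the two drug items by timing or setting but keep the class. For the disease item the class itself is narrower, and no reason is given.

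**Step 4. Ask which text governs screening.** D, D.3 and E.4 all refer to the inclusion and exclusion criteria. D.7 names those criteria as content of the cards or online material and does not mention the contraindications. The narrower wording is therefore the one in use when a patient is assessed.

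**Result.** As worded, the criterion applied at screening is narrower than both the contraindication and the exclusion stated in the safety section.

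**The case against.** The best reply is that there is one intended rule, loosely restated. Every item in the safety section's exclusion sentence departs from the lists. Its pregnancy wording reaches women who may become pregnant, while the lists say pregnant or lactating. Its aminoglycoside item drops the timing limit. Its blocking-agent item drops the anesthesia exception, although the same section says injections are given under general anesthesia. A sentence this loose is weak evidence of a separate eligibility rule. Myasthenia gravis, which the lists themselves give as a junction disease, is also the only disorder named anywhere. All of this stands, and it is why the point is minor. It does not dispose of the contraindication, which is stated separately and in the wider term.

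A second reply is to narrow the safety section to the junction instead. That section already names conditions with no matching criterion (pseudobulbar palsy and frequent chest infections), so it does not promise one-to-one matching. But those are called relative contraindications; neuromuscular disorder is stated without that qualifier. If the authors did mean only the junction, narrowing both safety statements would also be consistent. Widening the lists is the more cautious choice while the intent is unclear.

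Third, other safeguards exist. An attending physician judges eligibility (E.4), toxicity is checked at follow-up visits (D.3), and a data safety monitor can unblind (E.7). The highest dose per kilogram within Table 1 is 140 U / 45 kg = 3.1 U/kg for one limb, or 2 × 140 / 45 = 6.2 U/kg for two, against the 12 U/kg maximum that the safety section cites. These limit the consequence without settling the wording. One qualification: E.7 treats generalized weakness as common in trauma patients and considers only events beyond normal post-operative expectation, so monitoring is not a full substitute for exclusion at entry.

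**Conclusion.** The inconsistency is real on the text, and its severity is minor: a cheap, optional improvement to safety wording. It rests on reading neuromuscular disorder in its ordinary sense, as wider than the junction. The documents define neither term, so two phrasings of one concept remain possible.

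A reader might infer that the lists leave an identifiable at-risk group open to enrollment, or that some number of the 20 patients, or of the 10 assigned toxin, would be affected. The documents support neither. They name no disorder other than myasthenia gravis, which both lists already exclude, and they give no prevalence for any other. Nor do they show a route to harm, and an attending physician might exclude such a patient on judgment. No figure or analysis in the plan changes.

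**What to change.** In D.1 and E.2, replace the line with: *History of a neuromuscular disorder, including but not limited to disease of the neuromuscular junction (e.g., myasthenia gravis).* The phrase *including but not limited to* matters, because a criterion whose only examples are junction diseases could be read as no change. Carry the same line to the information cards and online criteria described in D.7. The disease wording in 5.6.a.1 then needs no edit.

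The cost is one line in two lists, made in one amendment and copied to the screening material. A rare otherwise eligible patient may be lost; the documents give no count. The wider term also asks more of the attending physician, who must judge what counts as a neuromuscular disorder.
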